8.1 Adverse Events

The following are specific definitions of terms guided by the International Conference on Harmonization (ICH E2) Guidelines for Good Clinical Practice (GCP) and the US Code of Federal Regulations (CFR) that apply to the following sections. The severity of AEs will be graded by the Common Terminology Criteria for Adverse Events (CTCAE), version 5 ([Appendix 4](#)).

Definition of Adverse Event:

An AE is defined as any new untoward medical occurrence or worsening of a pre-existing medical condition in a patient or clinical investigation subject administered an investigational (medicinal) product and that does not necessarily have a causal relationship with the product. An AE can therefore be any unfavorable and unintended sign (including an abnormal laboratory finding, for example), symptom, or disease temporally associated with the use of an investigational product, whether or not considered related to the investigational product.

AEs may also include pre- or post-treatment complications that occur as a result of protocol-specified procedures (eg, invasive procedures such as venipuncture, delivery procedure, etc). Pre-existing conditions that increase in severity or change in nature during (or as a consequence of use of a medicinal product in) the study will also be considered AEs.

An AE Will Not Include:

- Medical or surgical procedures (eg, surgery, endoscopy, tooth extraction, transfusion) for events that led to the procedure
- Pre-existing diseases, conditions, or laboratory abnormalities present or detected prior to the Screening visit, unless they worsen during the study
- Situations where an AE or untoward medical occurrence has not occurred (eg, hospitalization for elective surgery, social and/or convenience admissions)

Associated with the Use of the Drug (Causality):

There is a reasonable possibility that the event may have been caused by the investigational drug (and/or the administration procedure).

Unexpected Adverse Event:

Any event that is not identified in nature, severity, or frequency in the current version of the IB. For example, if the IB referred to elevated hepatic enzymes or hepatitis, then an event of hepatic necrosis would be considered unexpected by the virtue of the greater severity. The Sponsor or designee will determine AE expectedness.

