8.1.5 Adverse Event Severity and Relationship

Adverse event severity is defined as a qualitative assessment of the intensity of an AE as determined by the Investigator. The assessment of severity is made irrespective of the relationship or seriousness of the event to study treatment or the injection device.

In the absence of an assigned severity per the CTCAE v5.0 ([Appendix 4](#)) grading criteria, the Investigator will grade AEs according to the following severity criteria:

Mild/Grade 1: The event may be noticeable to subject; does not influence daily activities; usually does not require intervention.

Moderate/Grade 2: The event may be of sufficient severity to make subject uncomfortable; performance of daily activities may be influenced; intervention may be needed.

Severe/Grade 3: The event may cause severe discomfort; usually interferes with daily activities; subject may not be able to continue in the study; treatment or other intervention usually required.

Life- or Sight-Threatening/Grade 4: The event requires urgent intervention to preserve life and/or permanent loss of vision.

Death/Grade 5: The event resulted in the subject's death.

The relationship of study treatment (ie, Yutiq 0.05 mg), the injector, or the injection procedure, to each AE must be determined by the Investigator according to the following:

Not Related:	Evidence indicates no plausible direct relationship to the study treatment, device, or procedure, or there is a reasonable causal relationship between non-investigational product, concurrent disease, or circumstance and the AE; and/or a causal relationship is considered biologically implausible.
Possibly Related:	There is reasonable causal relationship between the study treatment, device, or procedure and the AE. There may or may not be a clinically-plausible temporal sequence between the onset of the AE and study treatment, device, or procedure; the AE is not reasonably supported by other conditions.
Probably Related:	The study medication, device, or procedure and AE occurrence are reasonably related in time; a clinically-plausible temporal sequence between the onset of the AE and study treatment, device, or procedure is likely; based upon the Investigator's clinical experience, the association of the AE with study medication, device, or procedure is likely; all other potential causes have been ruled out.

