8.2 Recording of Adverse Events

Medical conditions or diseases present before a subject starts study treatment are only considered AEs if they worsen after the start of the study treatment.

Adverse events may be spontaneously reported or elicited at each study visit through open-ended questioning, examination, or evaluation of a subject. To prevent reporting bias, subjects should not be questioned regarding the specific occurrence of one or more AEs.

The Investigator will record all AEs in the eCRF. Where a diagnosis is possible, it is preferable to report the diagnosis rather than a series of terms (signs/symptoms) relating to the diagnosis. If a definitive diagnosis is not possible, the individual symptoms and signs should be recorded.

The following information must be captured for all AEs:

- onset and end date
- severity
- seriousness
- relationship to study treatment or the injection device, procedure
- action taken

- any treatment required
- outcome

If treatment for the AE was administered, it should be recorded on the appropriate concomitant medication/procedure eCRF page. Each distinct AE should be recorded separately.

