11.4.6 Safety Analyses

Safety analyses will be performed on the Safety population at Weeks 24 and 52. Descriptive statistics will be provided for all treatment-emergent adverse events (TEAEs). Both ocular and non-ocular TEAEs are defined as events that start after the study drug administration, and occur before termination of the study, or were present before study drug administration and worsened after dose administration.

Frequency counts and percentage of subjects within each treatment group will be provided by using the Medical Dictionary for Regulatory Activities (MedDRA) system organ class (SOC) and preferred term (PT) by treatment. Within each level of summarization (SOC, PT), subjects who experience more than one occurrence will only be counted once. Adverse events will also be presented by severity (mild, moderate, severe, life- or sight-threatening), and by relationship to study drug (not related, possibly related, probably related). Listings of deaths, SAEs, and withdrawals due to AEs will be presented.

Clinical laboratory results will be presented by treatment group using descriptive statistics. Laboratory values will be listed by subject, and values outside of a normal reference range will be flagged. Pregnancy test results will be summarized separately.

Vital signs will be presented using descriptive statistics by treatment group and visit.

Subjective ocular tolerability and discomfort assessment results will be presented using descriptive statistics by treatment group and visit.

Prior and concomitant medications for both ocular and non-ocular indications will be coded using the World Health Organization (WHO) Drug Dictionary. These medications (prescription, OTC, and nutritional supplements) will be summarized by anatomical therapeutic chemical (ATC) classification levels, WHO generic name, and treatment group. Subjects will only be counted once at each level of the generic name or ATC level.

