1.1. Objectives and Endpoints

Objectives	Endpoints
Primary	Primary Efficacy Endpoint The proportion of subjects who have a recurrence of uveitis in the study eye within 24 weeks (6 months) after receiving study treatment
Secondary	Secondary Efficacy Endpoints 
• Proportion of subjects who have a recurrence of uveitis in the study eye within 52 weeks• Mean change from baseline in best corrected visual acuity (BCVA) letter score in the study eye at 24 and 52 weeks• Number of recurrences of uveitis within 24 and 52 weeks• Proportion of subjects with resolution of macular edema as measured by Spectral-domain Optical Coherence Tomography (SD-OCT) imaging at Day 28 and at Months 2, 3, 6, 9, and 12.
Safety	

	
• Systemic Adverse Events (AEs)• Ocular AEs, including IOP elevation• Medications/procedures required to control elevated IOP• Development or worsening of cataract• Cataract-related procedures• Clinically significant ocular changes• Procedure related AEs• Subjective ocular tolerability and discomfort assessments• Vital signs• Clinical laboratory assessments• Use of rescue and concomitant medications
--	--

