3.2. Safety Analysis Set

The Safety Analysis Set (SAS) will include all subjects who are randomized and received Yutiq 0.05 mg or sham injection. Subjects will be classified according to the actual treatment received. The SAS set will be used for the analysis of safety data.

4. Statistical Analyses

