4.4.2. Adverse Events

Adverse event data will be coded using the Medical Dictionary for Regulatory Activities (MedDRA). The severity of each AE will be graded by the investigator per CTCAE v5.0 criteria.

Descriptive statistics will be provided for all treatment-emergent adverse events (TEAEs). Both ocular and non-ocular TEAEs are defined as events that start after the study drug administration, and occur before termination of the study, or were present before study drug administration and worsened after dose administration.

Frequency counts and percentage of subjects within each treatment group will be provided by system organ class (SOC) and preferred term (PT) by treatment. Within each level of summarization (SOC, PT), subjects who experience more than one occurrence will only be counted once. Adverse events will also be presented by severity (mild, moderate, severe, life- or sight-threatening), and by relationship to study drug (not related, possibly related, probably related). Listings of deaths, and AEs leading to withdrawal will be presented.

Summaries will be sorted in descending order of frequency in the Yutiq 0.05 mg arm, when applicable. A listing of treatment-emergent AEs, treatment-emergent ocular events, and serious AEs will be provided.

Ocular Adverse Events

The following ocular events will be considered AEs for the purposes of this study:

- Decrease in BCVA of at least ≥ 15 letters or ≥ 3 lines from the previous BCVA measurement
- Moderate or severe (Grade 3 or 4) ocular findings compared to the last ocular examination
- Worsening of >2 steps in anterior chamber cell count or vitreous haze compared to the last ocular examination
- Increase in IOP of >10 mmHg at two visits at least 1 week apart or an increase in IOP to >25 mmHg

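### Procedure-related adverse events are a listed safety endpoint, but the SAP plans no summary of them: its only causality table is by relationship to study drug

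*SAP*

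**What the plan says.** SAP 1.1 gives "Procedure related AEs" its own line among the safety endpoints, and the protocol synopsis lists it too.

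Protocol 8.1.5 sets the assessment: "The relationship of study treatment (ie, Yutiq 0.05 mg), the injector, or the injection procedure, to each AE must be determined by the Investigator". Protocol 8.2 names, among the information required for every event, "relationship to study treatment or the injection device, procedure". The rating categories in 8.1.5 cover all three sources together; the one for a possible relationship reads "There is reasonable causal relationship between the study treatment, device, or procedure and the AE". Protocol 8.1 defines association with the drug as a reasonable possibility that the event "may have been caused by the investigational drug (and/or the administration procedure").

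SAP 4.4.2 plans treatment-emergent events by system organ class and preferred term, by severity "and by relationship to study drug (not related, possibly related, probably related"), together with listings. Protocol 11.4.6 has the same single causality display, "by relationship to study drug (not related, possibly related, probably related"). The SAP's safety set (3.2) "will include all subjects who are randomized and received Yutiq 0.05 mg or sham injection", so both arms appear in that table.

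**The concern.** An endpoint that is listed, and for which investigators supply the judgement, has no planned output. A programmer following SAP 4.4.2 would produce one causality table headed study drug and nothing labelled procedure-related.

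The heading of that table is a second difficulty. The SAP does not say which recorded item feeds it. If the item covers drug, injector and procedure jointly, the heading is inaccurate, and a reader could take injection complications for effects of the steroid.

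The distinction matters because the two procedures differ. Active treatment is a 25-gauge needle passed through the sclera (protocol 6.2, 6.2.1), while sham is a blunt needle pressed against it (6.4.3). A joint table would mix effects of the drug with effects of penetration, and the sham arm could not separate them.

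**Working it through.** No figure in the plan needs reproducing, and no sample size, error rate or event rate enters. The check compares the endpoint list, the collection rules and the planned displays.

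1. **Is the endpoint listed?** Yes, in SAP 1.1 and in the protocol synopsis.
2. **Is procedure causality assessed?** Yes. Protocol 8.1.5 and 8.2 require it for each event, alongside study treatment and the injector.
3. **Is a summary specified?** No. SAP 4.4.2 names relationship to study drug only, and no other SAP section defines or tabulates procedure- or injector-related events. Protocol 11.4.6 is also drug-only, so it does not fill the gap.
4. **Was the endpoint dropped on purpose?** The SAP introduction says that its endpoints and analyses are a reduced list because of early termination. Fellow-eye recurrence and time to recurrence are gone from that list; procedure-related events remain. SAP 4.8, which records changes to planned analyses, does not mention them.
5. **Are injection events missing from every count?** No. Every treatment-emergent event enters the class, term and severity tables whatever its causality. SAP 4.4.2 adds listings of treatment-emergent, ocular and serious events, and SAP 4.1.1 puts all study data in by-subject listings.
6. **What would the study-drug table contain?** This depends on the eCRF:

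| eCRF layout | Study-drug table | Procedure-related endpoint |
|---|---|---|
| Separate items for drug and for procedure or injector | Drug relationship, as headed | Rated, but not summarised |
| One combined item | Drug, injector and procedure events together, in both arms | Cannot be separated from the rest |

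The joint category wording in 8.1.5 and the definition in 8.1 point towards one combined item. They do not establish it: the texts in 8.1.5 and 8.2 join the sources with the word or, and neither specifies fields.

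Under both layouts the planned table fails to deliver the listed endpoint. Mislabelling arises only under the second.

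**The case against.** The strongest reply is that little is lost. All treatment-emergent events are counted by arm and listed, so an endophthalmitis or a painful injection will be visible. Steroid effects are also shown without any causality judgement, through intraocular pressure (SAP 4.4.4) and slit lamp findings (4.4.5). The analysis is descriptive with no hypothesis testing (4.1.1), so there is no formal comparison to distort. And since protocol 8.1 counts the administration procedure within drug association, the existing table may already include procedure-related events under an imprecise label.

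Much of this stands. A reader might infer that injection events are never counted; item 5 of the check shows otherwise. What is missing is the subset labelled as procedure-related.

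A reader might also infer that any event rated drug-related in a sham subject can only be procedural, because sham contains no insert. The documents do not support that. Under protocol 3.2, assessments after Day 1 are made by a masked investigator, who could in good faith attribute a sham subject's event to the drug until the 2022 unmasking. Such ratings carry information about attribution under masking, which is a reason to keep sham subjects in the drug table.

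What the reply does not do is supply the missing summary. If the table already includes procedure-related events, it cannot show them separately and its heading is wrong; if it does not, they have no table.

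**Conclusion.** The point holds as a gap between a listed endpoint and the planned output. One safety endpoint that the SAP chose to retain has no analysis, and the SAP leaves the source of its only causality table unstated. This rests on the text alone and is true whichever way the eCRF is built.

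The further claim, that drug and procedure events would be mixed under a study-drug heading, is conditional on a single combined eCRF item. The protocol's wording makes that plausible, but the eCRF is not in the documents, so it is a risk and not a finding.

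No numerical size can be given: the documents report neither event rates nor the number of subjects actually enrolled when recruitment stopped. Safety reporting is affected; the primary efficacy endpoint is not. The change is worth making because it is cheap and the investigators' judgements are already required by the protocol.

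**What to change.** In SAP 4.4.2, name the eCRF item or items that feed each causality table. Then:

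- **If separate items exist:** add a table of treatment-emergent events possibly or probably related to the injection procedure or injector, by arm in the SAP safety set, and identify it as the analysis of the listed endpoint. Keep drug relationship as a separate table, for both arms.
- **If only one combined item exists:** retitle the table as related to study treatment, injector or procedure, and state that procedure-related events cannot be separated from it.

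The cost is a few lines of SAP text and either one or two extra tables or a new title. No new data are needed.

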4.4.3. Subjective Ocular Tolerability and Discomfort Assessment

Ocular discomfort will be measured using a 6-point scale (from “absent” to “intolerable”) and ocular tolerability will be measured using a visual analog scale. Subjects will be asked to grade ocular tolerability and discomfort for the study eye and fellow eye at all study visits.

Subjective Ocular Discomfort Grading

Subjects will assess discomfort using the following subjective scale (Maca et al. 2010). This parameter will consist of questioning about superficial pain, foreign body, or gritty sensation, itching, burning, and other forms of non-specific discomfort.

- Grade 0: Absent
- Grade 0.5: Very mild
- Grade 1: Mild
- Grade 2: Moderate
- Grade 3: Severe
- Grade 4: Intolerable

Subjective Tolerability Using a Visual Analog Scale for Pain

Subjects will assess tolerability using the following subjective visual analog scale (Scoville et al. 1985). A visual analogue scale is performed by asking subjects to indicate on an unmarked 100-mm line the intensity of their pain. A mark of “0” represents no sensation while “100” indicates the worst imaginable pain. The location of the mark on the line is then measured with a ruler (in mm) to provide a numeric score.

The number and percentage of subjects in each ocular discomfort grading will be summarized by treatment group and visit. The VAS pain scale and change from baseline will be summarized using descriptive statistics by treatment group and visit.

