Eligibility determination, informed consent, demographics, medical and ophthalmic history (including a detailed history of the management of their uveitis over the previous 52 weeks), vital signs, clinical laboratory testing, ophthalmic examinations (includes BCVA, IOP, dilated ophthalmoscopy, and anterior, posterior and intermediate slit lamp examination), subjective ocular tolerability and discomfort assessment, concomitant medications, and pregnancy testing as appropriate.

Treatment Day (Day 1):

Eligibility confirmation including meeting the entry criteria for anterior chamber cells, vitreous haze, IOP, and visual acuity on Study Day 1, and then randomization to either intravitreal Yutiq 0.05 mg or sham injection. Following determination of study eye, subjects will receive either Yutiq 0.05 mg or the sham injection. Assessments on that day will include vital signs, ophthalmic examinations, spectral-domain – optical coherence tomography (SD-OCT), subjective ocular tolerability and discomfort assessment, pregnancy test if appropriate, concomitant medications, and adverse events (AEs).

Follow-up Visits:

Following injection on Study Day 1, subjects who were treated with Yutiq 0.05 mg will return for study visits on Days 7, 28, and at Months 2, 3, 6, and 12. Evaluations on these days will include: review of concomitant medications, vital signs, ophthalmic examinations, IOP, SD-OCT, subjective ocular tolerability and discomfort assessment, and AEs. All subjects treated with Yutiq 0.05 mg in the study will be followed for 52 weeks. In early May 2022, those subjects who had been treated with sham injection were discontinued from the study. Sham-treated subjects subsequently had their End of Study (EOS) evaluation.

Masking: Study subjects will receive either Yutiq 0.05 mg or a sham injection. Subjects and study staff conducting clinical study assessments, except for the clinician performing the injection procedure, will be masked to randomized treatment assignment.

Concomitant Medications:

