3 INVESTIGATIONAL PLAN

3.1 Overall Study Design

[figure not shown]
The protocol was originally planned to be a 52-week, prospective, randomized, masked (subject and outcome assessor), controlled, safety and efficacy study of intravitreal Yutiq 0.05 mg compared to sham injection with a primary efficacy and safety readout at 24 weeks.

The Sponsor has decided to stop enrollment for reasons other than safety or efficacy in early May 2022, following FDA advice received on January 24, 2022. The Sponsor is reevaluating the development program of Yutiq 0.05 mg. Subject enrollment has been stopped, and all subjects have been unmasked. Subjects who were randomized to the sham injection were discontinued from the study and underwent their EOS visit. Subjects who were randomized to sham injection may have been treated with standard of care medication, if necessary. Subjects who were randomized to Yutiq 0.05 mg will be followed on a modified protocol schedule through Month 12 (or ET) and evaluated for efficacy and safety.

As depicted in [Figure 3-1](#), subjects will receive either Yutiq 0.05 mg or a sham injection on Day 1 of the study. Subjects who were treated with Yutiq 0.05 mg will be assessed over the following 52 weeks on a modified protocol schedule according to the schedule presented in

Table 5–1. Subjects who were randomized to the sham injection were discontinued from the study and underwent their EOS visit.

Figure 3-1: Study Design Schema, Study EYP-2102-001

Note: The sponsor decided to stop enrollment for reasons other than safety or efficacy in early May 2022, following FDA advice received on January 24, 2022. The Sponsor is reevaluating the development program of Yutiq 0.05 mg. Subject enrollment in the study has been stopped. All subjects who were currently enrolled have been unmasked. Subjects who were to receive Yutiq 0.05 mg will be followed on a modified protocol schedule through Month 12 (or ET).

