6.1.	Appendix 1: List of Abbreviations.....	22
6.2.	Appendix 2: Supporting Study Information.....	23
6.2.1.	Disposition of Subjects.....	23
6.2.2.	Demographics.....	23
6.2.3.	Baseline and Disease Characteristics	23
6.2.4.	Protocol Deviations	23
6.2.5.	Medical History and Concurrent Illnesses	23
6.2.6.	Prior/Concomitant Medications	23
6.3.	Appendix 3: Data Handling Conventions	25
6.3.1.	Missing Date Imputation	25
7.	References	27

Version History

SAP Version	Date	Change	Rationale
1.0	08MAY2023	Not applicable	Original version

1. Introduction

This document presents the statistical analysis plan (SAP) for the protocol EYP-2102-001, a phase 3, multicenter, prospective, randomized, masked, controlled, safety and efficacy study of fluocinolone acetonide (FA) intravitreal 0.05 mg insert (Yutiq 0.05 mg) in subjects with chronic non-infectious uveitis affecting the posterior segment of the eye.

This SAP was developed in accordance with ICH E9 guideline. This SAP is to provide details of the statistical analyses based on the protocol version 3.0, dated July 20, 2022. The SAP will be finalized prior to database lock. Any deviations from the SAP after database lock and reasons for such deviations will be described and documented in the clinical study report.

The Sponsor decided to stop enrollment in early May 2022. Subjects who were randomized to Yutiq 0.05 mg will continue to be monitored on a modified-protocol schedule. The subjects who had been treated with sham injection were discontinued from the study. Consider the fact that the study was terminated early, the analyses described in this SAP has been limited to the scope per the interest of EyePoint Pharmaceuticals, Inc. For such a reason, the list of endpoints and analyses in this SAP is a reduced list from the study protocol.

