1.2. Study Design

The protocol was originally planned to be a 52-week, prospective, randomized, masked (subject and outcome assessor), controlled, safety and efficacy study of intravitreal Yutiq 0.05 mg compared to sham injection with a primary efficacy and safety readout at 24 weeks. A total of approximately 60 subjects (30 subjects in the Yutiq 0.05 mg group and 30 in the sham treatment group) were to be enrolled at approximately 40 sites in the US. One eye in each subject will be designated as the study eye.

The Sponsor decided to stop enrollment in early May 2022 for reasons other than safety or efficacy, following FDA advice received on January 24, 2022. Subjects who were randomized to Yutiq 0.05 mg will continue to be monitored on a modified-protocol schedule through Month 12 (or ET) and evaluated for efficacy and safety. Those subjects who had been treated with sham injection were discontinued from the study and subsequently had their End of Study (EOS) evaluation.

[figure not shown]
Subjects will receive either Yutiq 0.05 mg or a sham injection on Day 1 of the study on the study eye and will be assessed over the following 52 weeks according to the schedule of study procedures and assessment.

Yutiq 0.05 mg is a non-erodible intravitreal implant in a drug delivery system that contains 0.05 mg of FA and is designed to release FA at a rate of 0.25 µg/day into the vitreous humor for at least 6 months. Yutiq 0.05 mg is preloaded into a single-dose applicator to facilitate injection of the implant directly into the vitreous.

To ensure the health of both eyes, observations of both the study eye and non-study (fellow) eye

should be made at all visits as described in the schedule of study procedures and assessments. Ocular data will be collected for both eyes at all visits except for the SD-OCT assessments.

Figure 1. Study Design Schema

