4.3.2. Analytical Approach for Secondary Efficacy Endpoints

The secondary efficacy analyses will be conducted using the ITT analysis set based on observed data.

- The proportion of subjects with recurrent of uveitis will be summarized for the timepoint of interest using the same method described for the primary efficacy endpoint.
- The mean change from baseline in BCVA as measured by ETDRS letter score at each visit will be summarized for week 24 and 52 using descriptive statistics.

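### Yutiq rows for BCVA, discomfort and VAS can mix values given before and after subjects were unmasked; the SAP neither reports the unmasking nor marks the affected values

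*SAP*

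**What the plan says.** **Unmasking.** Protocol 3.1 states: "Subject enrollment has been stopped, and all subjects have been unmasked". The note to Figure 3-1 repeats it: "All subjects who were currently enrolled have been unmasked". Neither gives a date.

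**Sham arm.** The Protocol Synopsis (Follow-up Visits) says: "In early May 2022, those subjects who had been treated with sham injection were discontinued from the study". It adds: "Sham-treated subjects subsequently had their End of Study (EOS) evaluation".

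**Yutiq arm.** These subjects stay in follow-up to Month 12. The protocol is not consistent about their visits. The Synopsis and Table 5-1 list Days 7 and 28 and Months 2, 3, 6 and 12. Section 5.1 names only Months 6 and 12 (or early termination) for subjects followed after the stop.

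**SAP.** Sections 1, 1.2, 4.1.1 and 5 refer to the stop, but the unmasking appears nowhere. Section 4.8 lists two changes from the protocol, the dropped hypothesis test and the redefined populations, and does not list this one. Section 4.4.3 says: "The VAS pain scale and change from baseline will be summarized using descriptive statistics by treatment group and visit". Discomfort grades follow the same layout. Section 4.3.2 says: "The mean change from baseline in BCVA as measured by ETDRS letter score at each visit will be summarized", and Section 4.2.2 tabulates BCVA by arm at each scheduled visit. Section 4.1.3 uses nominal visits without re-mapping. Section 4.1.1 limits everything to descriptive summaries of observed data.

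**The concern.** Discomfort grade and VAS are pure self-report, and an ETDRS letter score depends partly on effort. Knowing that one received the implant can move all three. After the stop this can affect scheduled visits in one arm only, because sham subjects no longer had any. Change from baseline does not remove it: baseline is taken before treatment, so the knowledge enters only the later value.

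Subjective tolerability is a listed safety endpoint, and BCVA change is a secondary efficacy endpoint. If a Yutiq row contains post-unmasking values and the sham row beside it does not, the visible difference combines treatment with knowledge of treatment, and the table gives no sign of it. Values collected before unmasking are the only masked, concurrently randomised comparison left in the trial. The planned layout does not let a reader find them.

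The point is about measured and self-reported values. It does not concern whether a recurrence is attributed to uveitis.

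**Working it through.** The documents give no figure to reproduce. The check is date arithmetic under stated assumptions.

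**Inputs from the documents**
- Sham subjects discontinued in early May 2022 (Protocol Synopsis).
- Unmasking accompanied the stop. Discontinuing one arm alone requires that allocation was known by about then. The latest date by which it is on record is that of the protocol version cited in SAP Section 1: "This SAP is to provide details of the statistical analyses based on the protocol version 3.0, dated July 20, 2022".
- Randomisation was 1:1, so the enrolment pattern is taken as the same in both arms.

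**Assumptions**
- Uniform enrolment ending 5 May 2022 and starting between 1 June 2021 (n = 339 enrolment days) and 3 January 2022 (n = 123).
- Visits on their nominal day, d days after Day 1: Day 28, d = 27; Month 2, 61; Month 3, 91; Month 6, 183; Month 12, 365.
- Unmasking on 5 May 2022, or at the latest on 20 July 2022, which is 76 days later.
- All scheduled visits continued after the stop.

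**Formulas** (results limited to 0–100%)
- Share of Yutiq values on or after unmasking: (d + 1)/n for 5 May, (d − 75)/n for 20 July.
- Share of sham subjects who reached the visit before 5 May: 1 − (d + 1)/n.

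Month 6 as an example: 184/339 = 54% for the early start; 184/123 exceeds 1, so 100% for the late start. With 20 July: 108/339 = 32% and 108/123 = 88%.

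| Visit | Yutiq unmasked (5 May) | Yutiq unmasked (20 July) | Sham with a value before 5 May |
|---|---|---|---|
| Day 28 | 8–23% | 0% | 77–92% |
| Month 2 | 18–50% | 0% | 50–82% |
| Month 3 | 27–75% | 5–13% | 25–73% |
| Month 6 | 54–100% | 32–88% | 0–46% |
| Month 12 | 100% | 86–100% | 0% |

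**Three qualifications**

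1. *Schedule.* If Section 5.1 governs and only Months 6 and 12 took place after the stop, the unmasked share at Day 28, Month 2 and Month 3 is zero. The Month 6 and Month 12 lines stand under either reading.

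2. *Comparator.* If unmasking and discontinuation coincide, the Yutiq unmasked share and the sham share with a value add to 100%. A 100% row therefore has no sham beside it. With a 1 September 2021 start, Month 6 is 74% unmasked in Yutiq and 26% of sham have a value. With a 1 November 2021 start the figures are 99% and 1%. A mixed Month 6 row beside a usable sham row thus requires enrolment to have begun clearly before November 2021.

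3. *Sham rows.* They are masked only if unmasking did not precede discontinuation and the end-of-study values stay out of scheduled rows. SAP 4.1.3 does not re-map visits. Protocol 11.3.3 maps early termination to the next scheduled visit, and Table 5-1 puts early termination in the same column as Months 6 and 12.

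**Size of the shift.** If knowing the treatment moves a score by δ on average and a share p of the row is unmasked, the row mean moves by p × δ. At Month 6, with 5 May unmasking, that is 54% to 100% of δ. The documents give neither the size nor the sign of δ.

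**The case against.** The strongest reply is that nothing inferential depends on this. No hypothesis is tested, no between-arm estimate is planned, and all data will appear in by-subject listings. Enrolment stopped before completion, and SAP 4.8 itself gives insufficient sample size as the reason for dropping the test, so splitting rows would leave very small cells. This limits the consequence and argues against replacing the pooled rows. It does not remove the problem: the tables still print the two arms side by side, and the listings help only if they show which values came after unmasking.

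A reader might infer that the SAP presents the results as those of a fully masked trial, because Section 1.2 contains "masked (subject and outcome assessor), controlled, safety and efficacy study". The documents do not support that. The sentence introduces those words as the original plan, and the section goes on to report that sham subjects left. SAP 4.4.7.1 also no longer calls the medication review blinded, as Protocol 11.4.5 does. The SAP omits the unmasking; it does not claim that masking was kept.

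A reader might also infer that every Yutiq value from early May 2022 is unmasked and that all contrasts from Month 2 to Month 12 are affected. No unmasking date is given, Months 2 and 3 depend on an unresolved conflict over visits, and Month 12 probably has no sham row to compare with.

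**Conclusion.** The point holds as one of transparency and layout. Continuing Yutiq subjects were unmasked, these outcomes are open to influence from that knowledge, and the SAP neither discloses the unmasking nor separates the values.

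- **Month 6** is where mixing is most likely: 54–100% of Yutiq values with unmasking on 5 May 2022, 32–88% with 20 July 2022. A comparison with sham is affected only if some sham subjects had reached Month 6.
- **Months 2 and 3** may be affected if the Synopsis schedule applied after the stop, and are not if Section 5.1 did. The two passages must be reconciled.
- **Month 12** is probably all unmasked, with no sham row.

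These shares rest on assumed enrolment and unmasking dates. They also assume that subjects themselves, not only sites, learned the allocation, which is the plain reading of Protocol 3.1. No bias in millimetres or letters, and no direction, can be derived. Because the analysis is descriptive, the effect is confined to how the Yutiq and sham columns are read.

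**What to change.** 1. State the unmasking and its date in SAP 1.2, and list it in 4.8.
2. In SAP 4.1.1 define a flag for values obtained on or after unmasking. Use the subject's own date if recorded, otherwise the study-wide date. Protocol 3.5.1 requires a date when a code is broken in an emergency; no passage confirms that one was recorded per subject for this unmasking.
3. Keep the pooled rows. For BCVA change (4.2.2, 4.3.2), discomfort and VAS (4.4.3), add at each nominal visit a row limited to pre-unmasking values in both arms, and read any Yutiq–sham contrast from that row only.
4. Show the flag in the by-subject listings.
5. State that sham end-of-study values are flagged as unmasked and are not placed in a scheduled-visit row.
6. Reconcile the Synopsis and Table 5-1 with Protocol 5.1 on which visits took place after the stop.

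If the database is already locked, SAP Section 1 provides for documenting the change in the study report.

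The cost is one derived variable and a few extra rows. The drawback is small cells. Even if all 30 planned subjects per arm had been enrolled, the earliest assumed start and 5 May unmasking leave 46% × 30, about 14 per arm, in the pre-unmasking Month 6 row; later starts leave fewer, down to none.
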